## **INTRODUCTION**

### **Background and rationale**

The first-line treatment for idiopathic nephrotic syndrome in children is oral corticosteroids.[1] Most children experience several relapses of nephrotic syndrome, needing repeated courses of corticosteroid therapy or even more aggressive treatment with other immunosuppressive drugs. For most children, long-term prognosis is for complete resolution of their disease over time with maintenance of normal kidney function. Therefore, it is vital to focus on minimizing adverse events of the disease and its treatment. The aim of the RESTERN study (REducing STERoids in Relapsing Nephrotic syndrome) is to assess the safety and effectiveness of a reduced alternate day steroid schedule for treatment of a nephrotic syndrome relapse in comparison with the current standard therapy.

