### **Objectives**

Primary objective

To study the effectiveness of a reduced corticosteroid schedule for the treatment of a relapse in children with steroid sensitive nephrotic syndrome.

Secondary objectives

- To study the influence of maintenance immunosuppressive therapy on the effectiveness of a reduced steroid schedule for the treatment of a relapse in children with steroid sensitive nephrotic syndrome. Maintenance immunosuppressive therapies include levamisole, cyclosporine, tacrolimus, mycophenolate mofetil and mycophenolate sodium, and alternate day prednisolone with a maximum of 4 mg/m^2;
- To investigate the occurrence of relapses, frequency of relapses and progression to steroid dependent and frequent relapsing nephrotic syndrome in children with nephrotic syndrome under the standard treatment regimen;
- To study the influence of maintenance immunosuppressive therapy on the occurrence of subsequent relapses, frequency of subsequent relapses and progression to steroid dependent and frequent relapsing nephrotic syndrome under the standard regimen, and;
- To study the effectiveness of a reduced steroid schedule for the treatment of a relapse and occurrence and frequency of subsequent relapses in children with steroid dependent nephrotic syndrome.

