### **Randomisation**

After prednisolone 60 mg/m^2 daily in 1 dose until complete remission for 3 days, randomisation (allocation ratio 1:1) between:

- Standard treatment: 6 weeks prednisolone 40 mg/m^2 (max. 40 mg) every other day;

- Study treatment: 2 weeks prednisolone 40 mg/m^2 (max. 40 mg) every other day, then 4 weeks placebo every other day.

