### Baseline patient characteristics

Discrete variables will be demonstrated by frequencies and percentages. Continuously distributed variables will be demonstrated using either mean  $\pm$  standard deviation for data with normal distribution, or median and interquartile range for non-normally distributed data.

Table 2: Participant baseline characteristics

	Standard treatment (n = xxx)	Placebo (n = xxx)
Participant characteristics		
Male, n (%)	n/N (%)	n/N (%)
Age, years; median (IQR)	xx.x (xx.x to xx.x), n	xx.x (xx.x to xx.x), n
Age at onset, years; median (IQR)	xx.x (xx.x to xx.x), n	xx.x (xx.x to xx.x), n
Descent, n (%)	n/N (%)	n/N (%)

- Caucasian - Asian - African - Other, specify		
Maintenance therapy, n (%) - Levamisole - Cyclosporine - Tacrolimus - Mycophenolate mofetil - Mycophenolate sodium - Prednisolone	n/N (%)	n/N (%)
Total number of relapses prior to study participation	n/N (%)	n/N (%)
Number of relapses in preceding 24 months	n/N (%)	n/N (%)

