### **Analysis methods**

#### Primary endpoint

##### Time to first relapse after the final prednisolone dose

- As normal distribution is not assumed, the median time to relapse will be compared between the groups using a Mann-Whitney test;
- In case patients did not experience any relapse after 24 months or patients are lost to follow up before they experienced a relapse, incidence rates or person-time rates will be used to compare the groups;
- If a normal distribution is shown in the Shapiro-Wilk W test, a *t* test will be used;
- The percentages of study subjects with a relapse at 12 and 24 months will be compared between the groups;
- The cumulative probability on the absence of a relapse will be estimated by survival analysis, according to the Kaplan-Meier method. Log-rank tests are used for the comparison between the standard treatment group and placebo group;
- To test for the influence of factors, such as the use of maintenance immunosuppressive therapy, logistic regression analysis for nephrotic syndrome relapses with covariate analysis will be performed;
- Within each subject time to relapse after study medication will be compared to time to relapse before entering the study using a paired sample *t* test. This test will exclusively be performed in patients without changes in maintenance therapy.

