#### Secondary endpoints

##### Number of relapses after the final prednisolone dose

- Follow-up will be categorized into three periods (period 1, 0-12 months, period 2, 12-24 months, period 3, 0-24 months) and within each period, the number of relapses is counted;
- Poisson regression will be used to evaluate relapse rates in relation to treatment, maintenance immunosuppressive treatment, sex, age and period.

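### The Poisson model for relapse frequency has no term for relapse history, so its maintenance-therapy rate ratio is confounded by disease severity

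*SAP*

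**What the plan says.** - **Objective.** The third of the four secondary objectives (SAP, Objectives) begins "To study the influence of maintenance immunosuppressive therapy on the occurrence of subsequent relapses, frequency of subsequent relapses". It also covers progression of the disease, and it is set in children on the standard steroid schedule.
- **Model.** SAP, Secondary endpoints, Number of relapses after the final prednisolone dose: "Poisson regression will be used to evaluate relapse rates in relation to treatment, maintenance immunosuppressive treatment, sex, age and period". This is a closed list of five terms, and relapse history is not among them.
- **Data collected.** Table 2 (SAP, Baseline patient characteristics) has the row "Number of relapses in preceding 24 months" and a row for the lifetime count. No named regression model uses either.
- **What is randomised.** SAP, Randomisation: "randomisation (allocation ratio 1:1) between" two prednisolone schedules. Maintenance therapy is not allocated, and Eligibility admits children with and without it.
- **Why children receive it.** SAP, Background and rationale, describes most children as relapsing several times, "needing repeated courses of corticosteroid therapy or even more aggressive treatment with other immunosuppressive drugs".
- **Other model.** For the primary endpoint, "logistic regression analysis for nephrotic syndrome relapses with covariate analysis will be performed". Maintenance therapy is given there as an example of a factor, and no other covariate is named.

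**The concern.** By the SAP's own account, relapse history leads to the exposure. It can also be expected to predict the outcome, because children who relapsed often tend to go on relapsing. This is confounding by indication, and sex and age do not stand in for it. The maintenance coefficient then partly answers whether sicker children relapse more, which is not the objective. A drug that prevents relapses could be reported as having little or no effect, in a population where that finding could influence the choice of long-term therapy.

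**Working it through.** The SAP states no figure on this point, so there is none to reproduce. All inputs below are assumptions, shown over a range.

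**1. Closed form.** Take two severity levels. Let k be the relapse-rate ratio of severe to mild disease, and let p1 and p0 be the shares of severe disease among users and non-users of maintenance therapy. Without a severity term:

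observed ratio = true ratio × (p1·k + 1 − p1) / (p0·k + 1 − p0)

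| k | p1 / p0 | Bias factor | True 0.50 seen as | True 0.70 seen as |
|---|---|---|---|---|
| 1.5 | 60% / 40% | 1.30/1.20 = 1.08 | 0.54 | 0.76 |
| 2 | 60% / 40% | 1.60/1.40 = 1.14 | 0.57 | 0.80 |
| 2 | 70% / 30% | 1.70/1.30 = 1.31 | 0.65 | 0.92 |
| 3 | 70% / 30% | 2.40/1.60 = 1.50 | 0.75 | 1.05 |
| 3 | 80% / 20% | 2.60/1.40 = 1.86 | 0.93 | 1.30 |

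A harsher illustration sets rates of 4 and 1 relapses a year (k = 4), with half the children relapse-prone and a true ratio of 0.50:
- 80/20: 0.5 × 3.4/1.6 = 1.06
- 70/30: 0.5 × 3.1/1.9 = 0.82
- 60/40: 0.5 × 2.8/2.2 = 0.64

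The one half echoes the 50% in the SAP's Sample size section, and the 4 echoes its threshold for frequent relapse. Neither is a documented severity split or mean rate.

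**2. When the sign reverses.** The bias factor must exceed 1 / true ratio.
- True 0.50, 80/20: 0.5(0.8k + 0.2) > 0.2k + 0.8, so k > 3.5.
- True 0.50, 70/30: 0.5(0.7k + 0.3) > 0.3k + 0.7, so k > 11.
- True 0.50, 60/40: impossible, because the factor stays below 0.6/0.4 = 1.5 and 2 is needed.
- True 0.70, 80/20: 0.7(0.8k + 0.2) > 0.2k + 0.8, so 0.36k > 0.66 and k > 1.83.
- True 0.70, 70/30: 0.7(0.7k + 0.3) > 0.3k + 0.7, so 0.19k > 0.49 and k > 2.58.

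**3. What adjustment recovers.** Poisson models were simulated with 144 children, 24 months of follow-up and 200 replicates per scenario. A single 24-month window was used, so there was no period term. The SAP's other covariates were compared with the same set plus the log prior-relapse count.

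| Scenario | Share of look-back already on therapy | SAP covariates | Plus prior relapses |
|---|---|---|---|
| True 0.70, k = 3, 70/30 | none | 1.04 | 0.86 |
| | half | 1.06 | 0.94 |
| | all | 1.03 | 1.00 |
| True 0.60, k = 2, 60/40 | none | 0.69 | 0.67 |
| | all | 0.68 | 0.73 |

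Adjusting for true severity instead gave 0.69 to 0.71 in the first scenario and 0.59 to 0.60 in the second. The adjusted values also depend on the assumed relapse rates, so they show direction rather than forecast size. A separate simulation with assumed inputs agreed: 1.05 moved to 0.89 for a true 0.70, and a mild case went from 0.69 to 0.74 for a true 0.60.

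**4. The randomised comparison.** With no treatment effect simulated, the treatment rate ratio stayed at 0.98 to 1.02 with or without the prior-relapse term. In the separate simulation, adding the term cut the standard error of the treatment effect by about 2% to 13%.

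**The case against.** The strongest reply is that the remedy may not work. If a child was on maintenance therapy during the two years before entry, the therapy may already have lowered the count used for adjustment. The simulations bear this out: there was little gain when therapy covered the whole look-back, and a slightly worse estimate in a mild case. Relapse history from before maintenance began would be better, but the SAP does not show that it is recorded. This stands. It is a reason to show both estimates and to moderate the wording, not to leave the omission as it is. It can also be said that the model description speaks only of rates in relation to covariates, which is the language of association. The objective, however, speaks of influence.

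A reader might infer more than the SAP supports:

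- **That the effect will be reversed.** A true ratio of 0.50 does not cross 1 anywhere in the range k = 1.5 to 3; the worst case is 0.93.
- **That maintenance is coded by period, so that therapy started because of relapses counts as exposure for them.** The SAP does not say this. Under the primary endpoint it only restricts a before-and-after paired test to children whose maintenance therapy did not change. Eligibility and Table 2 treat maintenance as an entry characteristic. The coding is unstated, not shown to be wrong.
- **That the logistic model leaves out relapse history.** Its covariates are left open, so nothing is excluded.
- **That every maintenance objective is affected.** The first secondary objective asks whether the reduced schedule works differently by maintenance status. Within each stratum the treatment comparison is still randomised.
- **That relapse history is the strongest baseline predictor.** No section says so.

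**Conclusion.** The point holds for one secondary objective. As specified, the maintenance rate ratio is confounded by disease severity and can be diluted or hidden. Over the assumed range the inflation is 1.08 to 1.86, enough to bring a true 0.70 close to or past 1 under moderate to strong imbalance. Reversal needs a marked imbalance or a modest true effect. The direction follows from the SAP's own description of who receives these drugs, but the size does not, because the SAP gives neither the severity imbalance nor the drug effect. The primary endpoint and the randomised treatment comparison are not biased. The change is worth making because the covariate is already collected, but it reduces the confounding only in part.

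**What to change.** In the SAP section on the number of relapses after the final prednisolone dose:

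1. Add the Table 2 item "Number of relapses in preceding 24 months" to the Poisson model as a covariate and state its form (for example, the log of the count).
2. State that maintenance therapy is coded as status at randomisation.
3. Report the maintenance rate ratio with and without the new covariate, and note that the adjusted value may carry extra bias where therapy had already lowered the look-back count.
4. Give the same estimates within the standard arm, because the objective is worded for that schedule. With 72 children planned in that arm, they will be less precise than the pooled ones.
5. Describe the result as an observational association, not an effect of maintenance therapy.

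The cost is a few lines of SAP text and one covariate already recorded, with no new data. The SAP's Blinding section leaves room for final amendments at the blind review, so the change can be made before allocation is known. A side benefit is a modest gain in precision for the treatment comparison. The downside is that adjustment is partial and in some settings slightly harmful, which is why both estimates should be shown.

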### **Sample size**

From previous studies, we know the incidence of nephrotic syndrome in Dutch children to be 1.52/100,000 children/year.[2] Eighty percent of the pediatric patients develop at least 1 relapse of whom 50% continue towards frequent relapsing nephrotic syndrome. Based on data from previous studies, average time to relapse in the first year is approximately 185 days (standard deviation of 120 days).[3] Using the power calculation for a noninferiority trial with a continuous primary outcome, a power of 80% and a noninferiority limit of 50 days, 72 patients per group are required. Using a Cox Proportional Hazard time-to-relapse analysis (survival analysis)[4], similar numbers can be calculated.

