#### Secondary outcomes

##### 1. Number of relapses

- Definition: number of relapses per patient after the final prednisolone dose
- Timing: censored at 12 and 24 months
- Measurement value: number of patients (%)

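### The relapse-count model, read as written, gives one treatment rate ratio over 24 months, so the 12-month treatment comparison that the outcome definition asks for is not estimated

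*SAP*

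**What the plan says.** Under Secondary outcomes, item 1, the SAP defines the outcome as "number of relapses per patient after the final prednisolone dose" and gives its timing as "Timing: censored at 12 and 24 months". Two results are therefore expected, one for the first 12 months and one for the full 24.

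Under Analysis methods, Secondary endpoints, the data are cut as follows: "Follow-up will be categorized into three periods (period 1, 0-12 months, period 2, 12-24 months, period 3, 0-24 months". The third period is the sum of the first two. Relapses are tallied separately in each of the three.

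The analysis is then given in one sentence: "Poisson regression will be used to evaluate relapse rates in relation to treatment, maintenance immunosuppressive treatment, sex, age and period". The sentence does not mention an interaction, separate fits per period, a person-time offset or any handling of repeated records from one child.

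**The concern.** A period main effect lets the overall relapse rate differ between years. It does not let the treatment effect differ between years. A model with treatment and period as main effects has one treatment coefficient, and that coefficient applies to every period. The SAP cuts the data by year but names no term that uses the cut to compare the arms at 12 months.

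The arms differ by four weeks of alternate-day prednisolone near the start of follow-up (Randomisation section), so it is reasonable to ask whether any effect is larger in the first year. A constant rate ratio over 24 months is an assumption that the SAP does not state. If it fails, the planned model reports the 24-month average, and the 12-month result named in the outcome definition is absent.

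The Blinding section says that the final analyses can be done only after unblinding. How the 12-month comparison is obtained should therefore be written down before then.

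**Working it through.** **Inputs from the SAP.** Time points of 12 and 24 months (Secondary outcomes, item 1); three periods and the list of model terms (Analysis methods, Secondary endpoints); 1:1 allocation (Randomisation); 72 children per group (Sample size).

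**The SAP's own figure.** The SAP states no relapse rate, rate ratio or power for this model. Its only size figure is 72 per group, for time to relapse with SD 120 days and a limit of 50 days. At one-sided 5% and 80% power, 2 × (1.645 + 0.842)² × 120² / 50² = 71.3, rounded up to 72. It is used here only as the arm size.

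**Assumed inputs.** Control rates of 1.2 relapses per child in year 1 and 1.0 in year 2; treatment rate ratio 1.5 in year 1 and 1.0 in year 2; complete follow-up; a person-time offset. None of these is in the SAP.

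**Step 1: one stacked model or separate fits?** In a model fitted to one period only, period is constant and cannot be a covariate. Listing period as a term therefore implies one model over records stacked by period.

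**Step 2: what that model estimates.** With a log link, period terms, one treatment term and equal person-time in both arms, the fitted treatment ratio is the ratio of total counts. Expected relapses per child:

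- Reduced schedule: 1.2 × 1.5 + 1.0 × 1.0 = 2.8
- Standard schedule: 1.2 + 1.0 = 2.2
- Two yearly periods stacked: 2.8 / 2.2 = 1.27
- All three listed periods stacked, so that each relapse is counted twice: 5.6 / 4.4 = 1.27

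**Step 3: compare with the two results asked for.**

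- 0-12 months: 1.8 / 1.2 = 1.50, not reported
- 0-24 months: 2.8 / 2.2 = 1.27, the same as the single coefficient

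So the 24-month result is recovered and the 12-month result is not.

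**Step 4: range.** With a ratio of 1.0 in year 2, the single ratio is 1 + w × (RR₁ − 1), where RR₁ is the year-1 ratio and w the share of control relapses that fall in year 1. For four assumed pairs of control rates (years 1 and 2: 1 and 1; 1.5 and 1.5; 1.5 and 1.0; 2 and 0.7), w runs from 0.50 to 2 / 2.7 = 0.74:

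| True 0-12 month ratio | Single ratio reported |
|---|---|
| 1.25 | 1.13 to 1.19 |
| 1.5 | 1.25 to 1.37 |
| 2.0 | 1.50 to 1.74 |

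Models fitted to expected counts gave the same values. Adding treatment-by-period terms, or fitting each period separately, returned the true ratio for each period.

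**Step 5: constant ratio.** If the ratio is 1.5 in both years, (1.2 × 1.5 + 1.0 × 1.5) / 2.2 = 1.5. The single coefficient is then also the 12-month ratio.

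**The case against.** The strongest reply is that the sentence lists factors and is not a model formula. It does not exclude an interaction or per-period fits, and counting within a separate 0-24 month period suggests that per-period results may be intended. That is fair about intent. It does not settle the matter, because period has no place as a covariate in a per-period fit. If per-period results are meant, the SAP has to say so.

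Three stronger readings are tempting, and the document supports none of them.

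- *A reader might infer that the model gives neither the 12- nor the 24-month result.* It does give the 24-month ratio when follow-up is complete. In the example, 1.27 is the true 24-month ratio and not a biased figure.
- *A reader might infer that the plan averages an early harm with a year of no difference.* No section states an excess of relapses in year 1 or equality in year 2. The Interim analysis section allows only for an earlier first relapse. The pattern is a scenario.
- *A reader might infer that an early harm would be read as no difference.* Under the assumed rates, with 72 per arm and between-child gamma variance of 0.3 to 1.0, the chance of a significant result is 47-69% for year 1 alone and 24-41% for the 24-month count. Those figures need robust standard errors and a single 24-month count, and the SAP specifies neither. With the three overlapping periods stacked and ordinary Poisson errors, the same scenario is significant in 70-76% of trials, and a true null is rejected in 28-44%. That is a separate fault and it acts in the opposite direction. The comparison also sets a 12-month effect against a 24-month effect that is truly smaller.

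The consequence is limited too. Noninferiority is judged by a confidence interval against a margin, on time to first relapse. The primary analysis also compares relapse percentages at 12 and 24 months and uses Kaplan-Meier curves with log-rank tests. These cover first relapses and not counts, but they do look at the first year.

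**Conclusion.** The point holds for the 12-month comparison only. As written, the Poisson model yields one treatment rate ratio, which equals the 0-24 month ratio under complete follow-up. The 12-month ratio that the outcome definition calls for is not estimated.

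Under the assumed rates of 1.2 and 1.0, a 12-month ratio of 1.5 followed by 1.0 would appear as about 1.27; over the other rate pairs tried, it would appear as 1.25 to 1.37. All rates and ratios are assumptions, since the SAP gives none for counts. If the ratio is constant, nothing is masked.

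This is a gap between an outcome definition and its analysis, in a secondary outcome. It is not evidence of hidden harm and does not alter the noninferiority decision. It is worth correcting because the change is small.

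**What to change.** State in the SAP that the treatment rate ratio with 95% CI will be reported for two windows:

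- 0-12 months, from a separate model of the 12-month count, or from a treatment-by-period term fitted to the two non-overlapping years (0-12 and 12-24 months);
- 0-24 months, from a separate model of the 24-month count.

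The 0-24 month period should not be stacked with the two years it contains. The same sentence can state the person-time offset and how between-child variation or repeated records are handled.

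The cost is a change of wording and one model term or one extra fit; no new data are needed. The 12-month ratio will be less precise. With 72 per arm, the assumed rates, a ratio of 1 and Poisson variation only, the standard error of the log ratio is √(2 / (72 × 1.2)) = 0.152 at 12 months, against √(2 / (72 × 2.2)) = 0.112 at 24 months. At a constant ratio of 1.5 with robust errors, power is 69% at 12 months against 84% at 24 months for gamma variance 0.3, and 47% against 55% for variance 1.0. The 24-month ratio is still reported, so that precision is not lost.

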##### Development of frequent relapsing nephrotic syndrome (according to KDIGO criteria)

- This categorical outcome will be analyzed with either the Pearson chi-squared or Fisher exact test.

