## **STATISTICAL PRINCIPLES**

### **Level of confidence intervals and p-values**

For this noninferiority trial, the upper bound of the 2-sided 95% confidence interval for the treatment effect has to be below the margin to declare that noninferiority has been shown. P-values <0.05 will be considered statistically significant.

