##### 2. Progression to frequent relapsing nephrotic syndrome

- Definition (according to KDIGO criteria): four or more relapses in any 12-month period
- Timing: censored at 24 months
- Measurement value: number of patients (%)

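### Both progression outcomes get only a test of difference, with no between-arm estimate or confidence interval to show what excess under the reduced schedule remains possible

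*SAP*

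**What the plan says.** The trial is a noninferiority comparison whose aim is "to assess the safety and effectiveness of a reduced alternate day steroid schedule" (SAP, Background and rationale). Two secondary outcomes describe progression: frequent relapsing and steroid dependent nephrotic syndrome, both by KDIGO criteria and both censored at 24 months. Each has the same summary, "Measurement value: number of patients" with a percentage (SAP, Secondary outcomes 2 and 3).

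Under Analysis methods, Secondary endpoints, the whole analysis of frequent relapsing disease is "This categorical outcome will be analyzed with either the Pearson chi-squared or Fisher exact test". The entry for steroid dependent disease is worded identically. Neither names a risk difference, risk ratio, confidence interval or margin.

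The section on confidence intervals and p-values gives two rules. To declare noninferiority, "the upper bound of the 2-sided 95% confidence interval for the treatment effect has to be below the margin". For tests in general, "P-values <0.05 will be considered statistically significant". The only margin in the SAP is 50 days, for time to relapse (Sample size), so only the second rule can apply to progression.

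The Harms section uses the same pair of tests for adverse events but adds risk ratios and 95% confidence intervals where they can be computed.

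**The concern.** The question behind the trial is whether giving less prednisolone makes things worse. For a question of that kind, a test of no difference is informative mainly when it is significant. When it is not, the reader needs to know how large an excess the data still allow, and a p-value does not show that. The SAP meets this need for adverse events but not for the two outcomes that most directly describe a worsening disease course.

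At stake is how the secondary results read beside the primary claim. Two non-significant p-values for progression could look reassuring when the data are compatible with a substantial excess.

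**Working it through.** **Inputs from the SAP**
- Group size: "a power of 80% and a noninferiority limit of 50 days, 72 patients per group are required" (Sample size), with "randomisation (allocation ratio 1:1) between" the two arms (Randomisation).
- Standard deviation of time to relapse: "average time to relapse in the first year is approximately 185 days (standard deviation of 120 days").
- Significance level: 0.05, taken as two-sided for the progression tests.
- Rate of frequent relapsing disease: 50% of children who relapse (Sample size). No time horizon is attached.
- Rate of steroid dependence: none given.

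**Assumptions**
- All 72 per arm are evaluable.
- The 50% is used as the 24-month control rate of frequent relapsing disease.
- The control rate of steroid dependence lies between 10% and 30%.

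**Step 1. The plan's own figure.** n per group = 2 × [(z₁₋α + z₀.₈₀) × SD / margin]².
- One-sided α 0.05: 2 × [(1.645 + 0.842) × 120/50]² = 71.2, so 72. This reproduces the SAP.
- One-sided α 0.025: 2 × [(1.960 + 0.842) × 120/50]² = 90.4, so 91. This does not.

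The figure is used here only as the number per arm. It was derived for time to relapse; the SAP claims no power for progression.

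**Step 2. Normal approximation, frequent relapsing disease.** Power = Φ{[d√n − 1.96√(2p̄(1−p̄))] / √(p₁q₁ + p₂q₂)}, with n = 72.
- 50% v 60%: (0.8485 − 1.3790)/0.7000 = −0.758, so power is 22%.
- 50% v 65%: (1.2728 − 1.3703)/0.6910 = −0.141, so power is 44%.

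**Step 3. Exact check.** Enumerate all 73 × 73 outcome pairs under binomial(72, p) in each arm, and sum the probability that p < 0.05 for the uncorrected Pearson and the Fisher test. Miss rate = 1 − power.

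| Control rate | Excess | Missed, Pearson | Missed, Fisher |
|---|---|---|---|
| 50% | +10 | 76% | 81% |
| 50% | +15 | 55% | 61% |
| 40% | +10 | 76% | 81% |
| 40% | +15 | 55% | 61% |
| 30% | +10 | 76% | 81% |
| 30% | +15 | 54% | 61% |
| 20% | +10 | 71% | 78% |
| 20% | +15 | 47% | 55% |
| 10% | +10 | 61% | 68% |
| 10% | +15 | 32% | 40% |

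The 50% rows apply to frequent relapsing disease, and the 10-30% rows to steroid dependence. By the normal approximation, Pearson misses a 10-point excess more than half the time at control rates of about 5.5% or more, but a 15-point excess only at about 23% or more. At a 50% control rate, the difference detectable with 80% power is about 23 points.

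**Step 4. What an interval would add.** Suppose 36/72 progress on standard treatment and 47/72 on the reduced schedule.
- Difference: 0.653 − 0.500 = 15.3 points.
- Pearson z = 0.1528 / √[2 × 0.5764 × 0.4236 / 72] = 0.1528/0.0824 = 1.855, so p = 0.064.
- Wilson limits are 0.387 to 0.613 (36/72) and 0.538 to 0.752 (47/72).
- Newcombe lower limit: 0.153 − √(0.115² + 0.113²) = −0.8 points.
- Newcombe upper limit: 0.153 + √(0.100² + 0.113²) = +30.3 points.

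The test says "not significant"; the interval says that an excess of up to 30 points is not excluded. With equal counts of 36/72 in each arm, the interval is 0 ± 15.9 points.

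**The case against.** **Reading of a non-significant result.** A reader might infer that p > 0.05 is set to pass as proof of no more progression. The SAP does not say so. It ties noninferiority to a confidence bound and a margin, never to a non-significant p-value, and leaves the reading of the progression tests open. This part of the objection stands, and the point is limited to what the analysis omits.

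**Information already reported.** Counts and percentages per arm are planned, and a reader could derive a risk difference and interval from them. True, so nothing is irretrievably lost. But a pre-specified analysis should supply the estimate that answers the question, and the SAP does this for adverse events.

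**Other outcomes on disease course.** The relapse count is modelled by Poisson regression, and cumulative prednisolone is compared between arms. These bear on the disease course, and frequent relapsing disease is itself a dichotomy of relapse history. They do not replace an interval for the progression outcomes.

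**The miss rates.** It is tempting to say that a 10-15 point harm is missed more than half the time for both outcomes. That is not supported for steroid dependence: at control rates of 10-20%, Pearson misses a 15-point rise only 32-47% of the time. The 50% rate for frequent relapsing disease is also borrowed, since the SAP states it without a time horizon and the trial includes children on maintenance immunosuppression.

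**Low power is usual for secondary endpoints.** Agreed, and no power is claimed for them. No stated objective seeks noninferiority on progression; the Objectives section mentions progression only under the standard regimen. Low power is therefore not the fault. It is the reason for reporting an interval.

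**Conclusion.** The point holds as a minor one. For both progression outcomes the SAP plans a test of difference without a between-arm estimate or interval, while it plans both for adverse events.

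A non-significant test would carry little information about frequent relapsing disease: it is the more likely result under a true 10- or 15-point excess, given 72 evaluable per arm and the assumed 50% control rate. Control rates of 30% or 40% give nearly the same miss rates, so this does not hinge on exactly 50%. For steroid dependence it holds for a 10-point rise across the assumed 10-30% range, but for a 15-point rise only towards the upper end. Fewer evaluable children would lower power: at an assumed 50 per arm and a 50% control rate, power for a 15-point excess falls to about 33%.

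The primary noninferiority decision does not change.

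**What to change.** In the two Secondary endpoints entries for frequent relapsing and steroid dependent disease:

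1. Make the main result the risk difference (reduced minus standard) with a two-sided 95% score-based confidence interval, by Newcombe or Miettinen-Nurminen.
2. Keep the chi-squared or Fisher p-value as supportive.
3. State that the upper confidence limit will be reported as the largest excess not excluded, and that a non-significant test will not be taken as evidence of no increase.

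No margin or powered noninferiority test is asked for. At a 50% rate, a 15-point margin would need about 175 per arm.

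The cost is a few lines of SAP text and one further estimate per outcome from data already collected. The downside is wide intervals, with a half-width of about 16 points near a 50% rate, so the secondary results will look less reassuring.
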